3. AIM 2: PARTNER SELF-TESTING

3.1. OBJECTIVES

3.1.1. Primary Objectives:

- To determine whether providing index clients with HIV self-test kits for partners results in a greater number of partners tested as compared to optimized standard of care for partner notification and testing (referral slip)
- To determine whether providing index partners with HIV self-test kits is cost-effective compared to optimized standard of care using referral slips

3.1.2. Secondary Objectives:

- To assess the acceptability of giving self-test kits to index clients for partner testing
- To determine whether providing index partners with HIV self-test kits is superior to optimized standard of care in regard to identifying HIV+ partners (yield of testing)
- To determine whether providing index partners with HIV self-test kits is superior to optimized standard of care in regard to linkage rates among those who identify as HIV-positive
- To determine whether providing self-test kits to index clients and their partner is superior to optimized standard of care in regard to partner disclosure by the index client

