3.4.1.2 Baseline Visit for Index Client

A random sample of individuals will be screened and consented as they exit their ART visit. This will include ART clients who report having a sexual partner with an unknown HIV status. After written informed consent has been obtained, study staff will collect basic socio-demographics (including age, gender, marital status, and number of partners), HIV characteristics (date of HIV diagnosis, whether on ART and date started), and the number of eligible sexual partners who qualify for index testing referral slips. Individuals will also be asked whether they were offered a referral slip on the day of the survey.

Follow-up Visit of Index Clients

All index clients will be seen by study staff when they come for their next ART follow-up visit. A brief survey will be performed to collect information about whether the client disclosed their HIV status to their sex partner(s), whether they gave referral slips to their partner(s), and knowledge about whether partners completed a test, knowledge of their partner's test result, and knowledge about their partner's linkage to care. We will also survey the index client to determine whether any gender-based violence or fear of gender-based violence resulted from use of the self-tests. Index clients who do not return for their ART follow-up visit (more than two weeks late) will be traced through standard site protocols and surveyed either in the community or at the facility, if they return to care.

HIV testing registers will also be reviewed to measure the number of individuals tested through partner referrals and the proportion of partner referral tests who were identified as HIV-positive. All registry data will be anonymized. Records from partner notification clients aged 15 years and older will be included in the study. For those who are HIV-positive, the HTC and ART registers will be reviewed to determine if the patient started ART and presented for their four-week follow-up visit.

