4.2. Optimized Standard of Care Arm

4.2.1. Partner Notification and Referral

The study team will provide trainings, job aids, and regular mentorship to promote optimized standard of care in regards to partner notification and referral strategies for HIV-positive clients with partners who have an unknown HIV status. Under optimized standard of care, providers will ask clients at every ART visit whether they have current or recent (within 12 months) sex partners with unknown HIV status or tested negative for HIV more than 6 months ago. Clients will be counseled on the importance of partner notification and testing and given a partner notification slip to assist in partner notification and testing referral. Individuals will be counseled to ask their partners to return the referral slips when they come for testing. Partners who present at the facility for HIV testing will be tested in private rooms by trained HDAs following Ministry of Health guidelines. HDAs will ask all clients presenting for testing whether they were referred by a partner and this will be indicated in a column in the HIV testing register. Serial HIV testing will be performed with Determine and Uni-Gold as per standard of care. Those that test positive will be counseled and referred to ART services. ART initiation will follow standard clinic protocols under the universal treatment (Test and Treat policy).

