3.4.2.2 Baseline Visit for Index Client

A random sample of individuals will be screened and consented as they exit their ART visit. This will include ART clients who report having a sexual partner with an unknown HIV status. After written informed consent has been obtained, study staff will collect basic socio-demographics (including age, gender, marital status, and number of partners), HIV characteristics (date of HIV diagnosis, whether on ART and date started), and the number of eligible sexual partners who qualify for index testing referral slips. Individuals who consent will also be asked whether they were offered a referral slip on the day of the survey.

Follow-up Visit of Index Clients

All index clients will be seen by study staff when they come for their next ART follow-up visit. A brief survey will be performed to collect information about whether the client disclosed their HIV status to their sex partner(s), whether they gave referral slips to their partner(s), and knowledge about whether partners completed a test, knowledge of their partner's test result, and knowledge about their partner's linkage to care. We will also survey the index client to determine whether any gender-based violence or fear of gender-based violence resulted from use of the self-tests. Index clients who do not return for their ART follow-up visit (more than two weeks late) will be traced through standard site protocols and surveyed either in the community or at the facility, if they return to care.

HIV testing registers will also be reviewed to measure the number of individuals tested through partner referrals and the proportion of partner referral tests who were identified as HIV-positive. All registry data will be anonymized. Records from partner notification clients aged 15 years and older will be included in the study. For those who are HIV-positive, the ART register will be reviewed to determine if the patient started ART and presented for their four-week follow-up visit.

At the time of follow-up, a random sample of 40 index clients (20 men and 20 women) will be selected and asked to participate in semi-structured, in-depth interviews to explore the feasibility and acceptability of providing referral slips to partners, including challenges with disclosure and questions around harm or perceived risk of harm due to distributing the referral slip.

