3.4.4.2 Partner Self-Testing

Index clients will provide their partners with the following instructions verbally. The following instructions will also be provided on the referral form in picture form and in the local language:

1. Complete HIV self-test
2. If the self-test is positive, bring the self-test kit and referral card to the clinic for confirmatory testing and linkage to care.
3. If the self-test is positive and the client does not wish to present for further care, the self-test kit should be disposed of in the lockbox at the HSA house.
4. If the test is negative, the client will be instructed to dispose the self-test kit in a lockbox at the HSA house in the local community or may bring the kit to the lockbox at OPD/STI.

Any individual who has difficulty with the self-test kit or needs help with interpretation can come to the facility with the kit and the referral card and be seen by an HDA for assistance and/or standard of care HIV testing.

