3.4.4.3 Follow-up of Partner Self-Testing

The number of index partners tested will be determined based on the number of self-test kits returned to village and health facility lockboxes and triangulated with self-reports from a follow-up survey with the index client. Additionally, partners with a positive self-test kit who present to the facility for confirmatory testing and linkage to care, and/or partners who did not use the self-test kit but present to the facility for HIV testing will be accounted for through the returned referral cards. Like self-test kits, referral cards will be identified with a unique code, allowing the partner to be linked to the index client.

For those who are HIV-positive and present to the clinic for care, the ART register will be reviewed four weeks later to determine if the patient starts ART and presents for their four-week follow-up visit. All data from registers will be anonymized for use by the study team. In addition, index clients will provide self-reports about partner linkage to ART during a follow-up survey.

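### In the Aim 2 self-testing arm the ART register is read too early to record the four-week visit reliably, and the register window, time origin and denominator for linkage are not aligned across arms

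*Combined protocol and SAP*

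**What the plan says.** Section 3.1.2 makes linkage a secondary objective of Aim 2: self-testing is to be tested as "superior to optimized standard of care in regard to linkage rates among those who identify as HIV-positive".

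The register check is described separately for each arm.

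- **Self-testing (section 3.4.4.3).** The check applies to a restricted group, "For those who are HIV-positive and present to the clinic for care". For them, "the ART register will be reviewed four weeks later to determine if the patient starts ART and presents for their four-week follow-up visit".
- **Optimized standard of care (section 4.2, follow-up of index clients).** "For those who are HIV-positive, the ART register will be reviewed to determine if the patient started ART and presented for their four-week follow-up visit". No review time is given.
- **Standard of care (section 4.1, follow-up of index clients).** "the HTC and ART registers will be reviewed to determine if the patient started ART and presented for their four-week follow-up visit". Again no review time is given.

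Section 3.4.4.2 foresees partners with a positive self-test who stay away: "If the self-test is positive and the client does not wish to present for further care", the kit goes to a lockbox. In all three arms index clients are also asked at follow-up what they know of their partner's linkage. The Aim 2 statistical section (5.1) names partner testing and positivity as outcomes. It gives linkage no definition, window or analysis.

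**The concern.** A four-week visit cannot fall due until four weeks after ART starts. The self-testing arm's reading is timed from presentation, which is the same day as ART start at best. Followed as written, the rule would leave attended visits unrecorded because the register was read too soon, and those partners would look the same as partners who dropped out.

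The comparator arms collect the same two items under a rule with no stated timing. Section 5.1 does not supply a common definition that would override the arm-specific text. A difference in recorded linkage could then reflect when registers were read, and for whom, as well as what partners did.

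**Working it through.** The plan gives no figure for linkage, so there is nothing to reproduce. The check is a timing argument followed by an illustration.

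**1. Timing, with no assumed shares.** Count days from presentation. Let d be the day of ART start.

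- Reading: day 28.
- Visit due: day d + 28.
- Due by the reading only if d + 28 ≤ 28, that is d = 0.

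For d ≥ 1 the visit can be on record only if the partner attends early. For d = 0 the due date is the reading date, so attending one day late is missed. If the four weeks were instead meant to run from ART start, every partner would be in the d = 0 position, still with no margin.

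**2. Illustration on assumed inputs.** The documents give no interval from presentation to ART start. Section 4.2.1 refers to the Test and Treat policy without a same-day share. Assume a share s starts on the day of presentation, the others start after an exponential delay with mean m = 7 or 14 days (rounded up to whole days), and actual visit dates scatter around the due date with SD 3 days (rounded). The base is partners who do start ART and do attend the visit.

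- A same-day starter's visit is on record by day 28 with probability Φ(0.5/3) = 0.57.
- A later starter's visit is on record only through early attendance: simulated 0.13 for m = 7 and 0.08 for m = 14.
- Recorded share = 0.57s + r(1 − s), with r = 0.13 or 0.08.

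| Same-day share s | Visit due by day 28 | Visit recorded by day 28 |
|---|---|---|
| 0% | 0% | 8–13% |
| 50% | 50% | 32–35% |
| 90% | 90% | 52% |
| 100% | 100% | 57% |

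**3. ART start is much less affected.** The share of starts recorded by day 28 is s + (1 − s)(1 − e^(−28/m)). At s = 0 this is 1 − e^(−4) = 0.98 for m = 7 and 1 − e^(−2) = 0.86 for m = 14. The range over s is 86–100%.

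**4. Later readings.** On the same inputs the visit is recorded for 86–100% by day 56 and 98–100% by day 84. At day 70 (10 weeks) it is due for those who started by day 42. At s = 0 that is 1 − e^(−42/14) = 0.95 or 1 − e^(−42/7) = 0.998.

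**5. Denominator.** In the comparator arms the check follows partner-referral tests in the facility register, so a partner known to be positive there has already attended. In the self-testing arm, presenting is a further step after a positive result, and only those who take it are checked. If 70% of presenters link (assumed), the rate among all HIV-positive partners depends on the share who present:

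- 40% present: 0.40 × 0.70 = 28%
- 60% present: 0.60 × 0.70 = 42%
- 80% present: 0.80 × 0.70 = 56%

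The register check would show 70% in each case, so this element can raise apparent linkage under self-testing while the early reading lowers recorded visits.

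**The case against.** The strongest reply is that the text shows less than a reader might infer. A reader might conclude that the comparison is biased against self-testing, because its visit is not yet due for most partners while the comparator registers are read without limit. The documents do not support that reading.

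- **Comparator timing is unstated, which does not make it open-ended.** The same four-week check may be intended and not repeated. A timing bias between arms needs later reading in the comparators, and no section says so.
- **That the visit is not yet due for most partners** would need fewer than half to start ART on the day they present. No section gives that share.
- **Linkage is nowhere defined as the visit.** ART start is the other recorded item and is little affected.
- **There is a second source.** Index clients report on partner linkage in all arms, independently of the day-28 reading. It is second-hand, but it is common to the arms.
- **The denominator may act the other way**, as step 5 shows.
- **The two-week lateness margin** in the follow-up text is a tracing trigger for index clients. It is not evidence of how late newly diagnosed partners attend.

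These points stand, and they remove any claim about direction. A reader could also put a figure on a deficit. If 80% truly attend within two weeks of the due date, and the recorded share is 0.5 × 0.5 = 25%, 0.7 × 0.5 = 35% or 1.0 × 0.7 = 70%, the shortfall is 55, 45 or 10 points. Every share there is assumed, the shortfall concerns the visit only, and it becomes a difference between arms only if comparator registers are read later.

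The reply does not rescue the day-28 rule. If the comparators are read later, the visit is under-recorded in one arm. If they are read at day 28 too, it is poorly measured in all three.

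**Conclusion.** The point holds in a limited form. Reading the register four weeks after presentation comes before the four-week visit is due for anyone not starting ART that day, and it leaves no margin for the rest. This needs only the natural reading that the four weeks run from presentation. The size depends on assumptions: about 8% to 57% of attended visits on record at day 28 in the illustration, against 86% to 100% of ART starts.

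The register window, time origin and denominator are also not aligned across arms. The linkage comparison may be biased, but neither the direction nor the size of a difference between arms can be fixed from the documents. Because the stated rule would itself under-record a stated outcome, this is more than a missing detail. It affects a secondary objective and leaves the primary partner-testing outcome untouched, so the change should be made but is not critical.

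**What to change.** In section 3.4.4.3 and in the index-client follow-up text of sections 4.1 and 4.2, use one definition of linkage, and carry it into section 5.1:

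- **Time origin:** date of the facility HIV-positive test, in every arm.
- **Two outcomes, reported separately:** (a) ART start within a fixed window; (b) attendance at the four-week visit, counted from the recorded ART start date, with a stated lateness allowance.
- **Abstraction:** no earlier than the close of both windows, in every arm. One example is 4 weeks to start + 4 weeks to the visit + 2 weeks' lateness = 10 weeks after the positive test. The lengths are the sponsor's choice; the two weeks borrow the margin already used for tracing index clients.
- **Denominator:** anchoring on the facility test gives the register comparison a like base. Anchoring alone still leaves out self-test positives who never present, so report them separately, as far as index-client reports (and returned kits, if these are read) identify them.

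This alters when and for whom registers are read, and nothing about care. The cost is three edited passages, a short addition to section 5.1 and later abstraction: 10 − 4 = 6 weeks later for the last partners, unless those partners are excluded equally in all arms.

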3.4.4.4 Follow-up Visit of Index Clients

All index clients will be seen by study staff when they come for their next ART follow-up visit. A brief survey will be performed to collect information about whether the client disclosed their HIV status to their sex partner(s), whether they gave self-test kits to their partner(s), and knowledge about whether partners completed the test, knowledge of their partner’s test result, and knowledge about their partner’s linkage to care. We will also survey the index client to determine whether they were able to successfully show their partner(s) how to use the kit and whether any gender-based violence or fear of gender-based violence resulted from use of the self-tests. Index clients who do not return for their ART follow-up visit (more than two weeks late) will be traced through standard site protocols and surveyed either in the community or at the facility, if they return to care.

A random sample of 40 index clients (20 men and 20 women) and 40 index partners (20 men and 20 women) will be selected and asked to participate in semi-structured, in-depth interviews to explore the feasibility and acceptability of providing self-test kits to partners, including challenges with disclosure and questions around harm or perceived risk of harm due to distributing the kits.

2.4.4.5 *Follow-up Visits with Index Partners*

Index partners will be recruited for in-depth interviews through index clients (n=40). During follow-up visits with index clients, a random subset of clients will be given a study invitation card to be given to their sexual partner who was given a self-test kit. The study invitation card will describe the in-depth interview they are being recruited for and provide a study-specific phone number the index partner can call in order to participate in the study. In addition, index clients will be asked if the study team could call the randomly selected partner to discuss the study. Index clients will be told the purpose of the call. If index clients give permission to contact the index partner, up to 2 phone numbers will be collected. Index partners will be called up to 3 times over a 2-week period for recruitment into the study. If the index partner cannot be reached after the third try, the partner will be listed as “unreachable” and excluded from the study.

For index partners contacted by the study staff, oral consent for screening and eligibility screening will take place via phone. Those who agree and are deemed eligible for the study will decide on a time and place for completing full oral consent to participate in the study and completing one in-depth interview. Interested respondents will choose the location of their choice, either at the facility or in their local community. Interviews will last approximately 60 minutes. Interviews will provide additional information about the feasibility and acceptability of providing self-test kits to partners, including challenges with completing the test, questions around harm or perceived risk of harm, and challenges linking to care at health facilities.

5. STATISTICAL METHODS

5.1. Outcome Measures

3.5.1.1 Sample Size and Statistical Analysis for Primary Outcome Measures

We will have 15 clusters (facilities) available for randomization, and therefore, estimated our sample size assuming a fixed number of clusters (k) and an equal number of clusters per arm. We also assumed an equal number of participants per cluster. The below calculations were determined using a minimum sample size. Assuming a type I error of 0.05, an intracluster correlation of 0.004 and sample sizes of 600 HIV-positive patients per arm, we have 89% power to detect a difference in testing coverage of 20% in study arm 2 (optimized standard of care) and 40% in study arm 3 (self-testing). Because we are uncertain about the proportion of partners who will test under each arm, we have considered a range of possibilities, with the majority of scenarios providing at least 87% power to detect a difference between the two arms of interest (optimized standard of care and self-testing) (Figure 4).

We will calculate descriptive statistics, including mean/median, variation (standard deviation, kurtosis), range, and frequency distributions for the demographic and clinical characteristics, overall and by study arm. The outcomes of interest include the proportion of partners tested and HIV-positivity of partners. Differences in the prevalence of each of the outcomes of interest will be examined by study arm as well as by other factors of interest including demographic characteristics (e.g., age, gender), clinical characteristics (e.g., reason for clinic visit), and structural factors (e.g., geographic location). The differences will be evaluated using t-tests, Mann-Whitney U test (or other non-parametric tests), chi-square methods, and Fisher's exact test as appropriate. In order to assess factors associated with partner's HIV testing/positivity, we will use hierarchical linear models in order to account for clustering of effects within each clinic. Separate models will be developed for each outcome of interest and covariates of interest include patient characteristics (e.g., age, gender) and other structural and contextual factors.

Qualitative Analysis for Secondary Outcome Measures

Our secondary outcomes measured will be feasibility and acceptability of partner self-testing, privacy concerns, problems with performing or interpreting self-tests, and perceived harms or benefits resulting from self-testing. Qualitative methods (semi-structured in-depth interviews) will be conducted on a subset of index clients ($n=30$) from the partner self-testing arm and 30 from the optimized standard of care arm ($n=30$). Qualitative methods will be the same as those outlined in Aim 1.

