HIV Testing Services Program Officer
Ministry of Health, Dept of HIV/AIDS
Lilongwe, Malawi
Tele: [name]
Email: [contact]

[name]
Research Coordinator
Partners in Hope
[name], Lilongwe, Malawi

Use of HIV Self-Test Kits to Increase Identification of HIV-Infected Individuals and Their Partners

SCHEMA

Purpose: To evaluate the feasibility and cost-effectiveness of self-testing strategies within health facilities compared to standard of care in the following settings:
(1) group self-testing in outpatient departments (OPD) and sexually transmitted infection (STI) clinics compared to standard of care and optimized standard of care HIV testing and counseling; and
(2) self-testing for partners of HIV+ index clients compared to standard of care and optimized standard of care partner notification strategies.

Design: Unblinded cluster-randomized controlled trial

Study Population: Aim 1: Individuals 15 years of age and older not already known to be HIV-positive
Aim 2: HIV-positive individuals 15 years of age and older with at least one sexual partner with unknown HIV status

Sample Size: **Aim 1: 15 clusters with a total of 15,000 participants (5,000 per arm, 1,000 per site)**
Aim 2: 15 clusters with a total of 7,500 participants (2,500 per arm, 500 per site)

Intervention: Aim 1: To test the feasibility and cost-effectiveness of group HIV self-testing in outpatient department (OPD) and sexually transmitted infections (STI) clinics

- Arm 1: Standard of care for provider-initiated testing and counseling (PITC)
- Arm 2: Optimized standard of care for PITC
- Arm 3: Group HIV self-testing

Aim 2: To test the feasibility and cost-effectiveness of partner HIV self-testing

- Arm 1: Standard of care for partner testing
- Arm 2: Optimized standard of care for partner testing
- Arm 3: HIV self-testing

Study Duration: Approximately 18 months total

Aim 1: To test the feasibility and cost-effectiveness of group HIV self-testing for patients in waiting areas of outpatient department (OPD) and sexually transmitted infections (STI) clinics

Primary Objectives:

- To determine whether group self-testing in waiting areas of OPD and sexually transmitted STI clinics is superior in regard to number of individuals HIV tested compared to optimized standard of care (provider-initiated testing and counseling; PITC)
- To determine whether group self-testing in waiting areas of OPD and STI clinics is cost-effective compared to optimized standard of care using PITC

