3.2. STUDY POPULATION

This study will be conducted among approximately 1,800 individuals 15 years or older who have at least one sexual partner with unknown HIV status. The study population may include participants from Aim 1 who test HIV-positive under any of the three study arms.

The study will be conducted in the same 15 clusters used in Aim 1. The cluster randomization will be retained for Aim 2 such that sites identified as intervention sites for Aim 1 will remain intervention sites for Aim 2 (likewise for standard of care and optimized standard of care sites).

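### Aim 2 sample size and power do not agree: the total is 7,500 in one place and about 1,800 in another, and the stated inputs give power above 99.9%, not 89%

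*Combined protocol and SAP*

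**What the plan says.** The combined protocol and SAP gives the size of Aim 2 in three places.

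- Schema, Sample Size: "Aim 2: 15 clusters with a total of 7,500 participants (2,500 per arm, 500 per site").
- Section 3.2, Study Population: "This study will be conducted among approximately 1,800 individuals 15 years or older".
- Section 3.5.1.1, the Aim 2 sample size paragraph: "sample sizes of 600 HIV-positive patients per arm", introduced by "The below calculations were determined using a minimum sample size".

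The same paragraph of section 3.5.1.1 takes a type I error of 0.05 and gives the other power inputs with the result: "an intracluster correlation of 0.004 and sample sizes of 600 HIV-positive patients per arm, we have 89% power to detect a difference". The coverage compared is 20% in arm 2 against 40% in arm 3. It assumes 15 facilities, the same number in each arm and the same number of participants in each facility. It names no power formula, does not say whether the test is one- or two-sided, and makes no allowance for loss to follow-up.

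**The concern.** There are two separate problems.

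First, 7,500 and about 1,800 are both given as the size of Aim 2. Section 6.3, headed Sample Size and Accrual, commits the team to act when a site falls short of its projections, but it contains no number. A facility with 150 index clients would have passed 120, yet would have reached only 30% of 500 (150/500).

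Second, 89% looks far too low for a 20-point difference with 600 per arm and so small an ICC. If it does not follow from the inputs, then either the power or one of the inputs is misprinted. Which one it is matters. If the ICC is right, 600 per arm is far more than this contrast needs. If a larger ICC was used, the printed ICC is wrong and the true margin is thinner than the printed inputs suggest.

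**Working it through.** **Inputs.** All are from section 3.5.1.1 unless noted.

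- n = 600 per arm.
- k = 5 facilities per arm (15 divided equally by 3), so m = 600/5 = 120 per facility.
- ICC = 0.004; type I error 0.05, taken as two-sided.
- p1 = 0.20 (arm 2), p2 = 0.40 (arm 3).
- One outcome per index client, with full follow-up (assumption).

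**Totals.** 3 × 600 = 1,800, which is the section 3.2 figure. 3 × 2,500 = 15 × 500 = 7,500, which is the schema figure. 7,500/1,800 = 4.2.

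**Attempt to reproduce the 89%.**

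- Design effect = 1 + (m − 1) × ICC = 1 + 119 × 0.004 = 1.476.
- Effective n = 600/1.476 = 406.5 per arm.
- Standardised difference = 0.20/√[(0.16 + 0.24)/406.5] = 6.38.
- Pooled z: power = Φ{[0.20 × √406.5 − 1.96 × √(2 × 0.30 × 0.70)]/√0.40} = 99.999%.
- Noncentral t: 99.98% with 8 df (10 facilities − 2 arms) and 99.99% with 12 df (15 facilities − 3 arms).

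The stated type II error is 11%; the computed one is at most 0.02%.

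**Other readings at 0.004, each taken alone.**

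| Reading | Power |
|---|---|
| One-sided test | >99.999% |
| Continuity correction | 99.999% |
| Alpha divided by 3 | 99.996% (z) |
| Half the sample lost (300 per arm; design effect 1.236, effective n 242.7) | 99.8% (pooled z), 99.0% (t, 8 df) |
| 600 as the three-arm total (200 per arm) | 98.4% (pooled z), 95.2% (t, 8 df) |
| 0.004 as between-facility variance | 98.7% (z), 95.5% (t, 8 df) |
| Schema size, 2,500 per arm | >99.9999% |

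None comes near 89%.

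**What would give 89%, with everything else as stated.**

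- ICC of 0.0398 (pooled z), 0.0413 (unpooled z), 0.0333 (t, 12 df) or 0.0295 (t, 8 df); or
- about 114 per arm (pooled z) or 148 (t, 8 df); or
- 20% against 29.6% (pooled z) or 31.1% (t, 8 df).

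**The decimal-slip hypothesis, ICC = 0.04.** At 600 per arm the design effect is 1 + 119 × 0.04 = 5.76, the effective n is 104.2 and the standardised difference is 3.23.

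| Per arm | Pooled z | t, 12 df | t, 8 df |
|---|---|---|---|
| 2,500 | 92.6% | 88.6% | 85.5% |
| 600 | 88.9% | 84.2% | 80.6% |
| 480 (20% lost) | 87.6% | 82.7% | 79.1% |
| 300 (50% lost) | 83.6% | 78.3% | 74.5% |

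**Control on the method.** The same calculation on the Aim 1 statement in section 2.5.1 (5,000 per arm, ICC 0.004, 5% against 10%) gives a design effect of 4.996, an effective n of 1,000.8, and power of 98.9% (z) or 96.0% (t, 8 df). The claim there of 95% or more holds, so the method is not what makes the Aim 2 figure fail.

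**The case against.** The best defence on the totals is that section 3.5.1.1 says its calculation uses a minimum. A planning minimum of 1,800 beside a larger target of 7,500 is coherent. This explains why power was run at 600 per arm. It does not reconcile the totals, because section 3.2 presents about 1,800 as the study population, without calling it a minimum and without mentioning 7,500.

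On power, the defence is that the error is harmless: on the printed inputs the plan understates its power, and no endpoint, comparison or analysis changes. That is fair, and it is why the point does not amount to a claim of low power. A stated figure that its own inputs contradict still has to be corrected, and the one simple substitution that recovers it makes the position less comfortable.

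Three limits also stand. Site projections and site procedures (sections 6.3 and 8.2) may carry a single target that is not reproduced here, so what can be said is that this document gives none. The t-based figures are a reviewer's addition, since the plan names no power method; they bear on the conclusion only if the larger ICC was used. With an ICC of 0.04, power of 80% or more on the t test with 8 df depends on nearly full follow-up.

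**Conclusion.** Both parts hold. The Aim 2 total is given as 7,500 and as about 1,800 (500 or 120 per site) without reconciliation. The stated 89% does not reproduce: the printed inputs give 99.98% to 99.999%, and no single alternative reading tried at 0.004 falls below 95%. At least one of the ICC, the power or another stated input is wrong as written.

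An ICC of 0.04 gives 88.9% and is a plausible source, but that is an inference. With full follow-up, either sample size with either ICC (0.004 or 0.04) gives at least 80% power for 20% against 40%, so underpowering is not shown. The results assume equal facility sizes, a two-sided test and one outcome per index client. Figure 4 is not visible in the text reviewed, so nothing is concluded about its scenarios.

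**What to change.** 1. Give one Aim 2 sample size in the schema, section 3.2 and section 3.5.1.1, with matching per-arm and per-site numbers. Alternatively, label 1,800 as the minimum and 7,500 as the target wherever they appear. Put the per-site target in section 6.3.
2. In section 3.5.1.1, state the ICC, power formula and sidedness actually used, and any allowance for loss, then correct whichever figure is wrong.
   - If the ICC is 0.004, restate power as above 99%.
   - If it is 0.04, correct the ICC, say that 89% is a normal approximation, give the value that allows for few facilities (about 84% with 12 df or 81% with 8 df, before any loss), and say why it differs from the 0.004 used for Aim 1.
3. Recheck the Figure 4 scenarios on the same inputs. A smaller ICC would not break the stated lower bound of 87%.

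The Aim 1 power statement needs no change unless its ICC is revised. The cost is a few sentences of text, with no additional participants for the power correction. If the ICC proves to be 0.04, the restated power will look less favourable.
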